#### 6. DOSE MODIFICATIONS

Individually, each subject will be allowed up to dose-reduce to 75 mg infigratinib, as follows (see also Table 5).

- If a subject's infigratinib dose is 125 mg, 2 dose reductions of infigratinib are permitted.
- If a subject's infigratinib dose is 100 mg, 1 dose reduction of infigratinib is permitted.
- If a subject's infigratinib dose is 75 mg, no dose reduction of infigratinib is permitted, with infigratinib treatment discontinuation the only option.

Subjects should discontinue infigratinib if toxicities persist following dose reductions to the lowest level allowed, unless it has been discussed and approved by the QED Therapeutics' Medical Monitor.

Following resolution of toxicity to baseline or  $\leq$  Grade 1, or  $\leq$  Grade 2 for hematologic toxicities, treatment is resumed at either the same or lower dose of study drug as per the criteria in Table 6. Adverse event lab abnormalities outlined in Table 6 should be followed at least weekly until the specified resolution. If treatment is resumed at the same dose of study drug, and the same toxicity recurs with the same or worse severity regardless of duration, dose must be reduced to the next lower dose level. If treatment is resumed at the lower dose of study drug, and the same toxicity recurs with the same or worse severity, the subject should have a second dose reduction.

Subjects who are withdrawn from the study for a study related AE or an abnormal laboratory value must be followed as described in Section 7.3.

**Table 5.** Dose Modification Scheme for Infigratinib

Dose Reduction			
	Dose level 3	(Starting) Dose level 2	Dose level 1
Infigratinib	125 mg	100 mg	75 mg

In exceptional situations, study drug may continue even if the subject experienced one of the treatment stopping rules. The decision to allow for continuation of treatment will be made on a case-by-case basis following discussion between QED Therapeutics and the investigator.

**Table 6.** Criteria for Interruption and Re-initiation of Infigratinib for AEs Considered to be Possibly Related to Infigratinib

Worst Toxicity CTCAE (v5.0) Grade (Unless Otherwise Specified)	Recommended Dose Modifications any Time During a Cycle of Therapy					
CARDIAC DISORDERS						
Cardiac - Prolonged QTcF Interv	Cardiac - Prolonged QTcF Interval					

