Grade 3 (ANC < $1.0 \times 10^9$ /L, single temperature of > $38.3^{\circ}$ C or a sustained temperature of $\geq 38.0^{\circ}$ C)	
 
Hold dose of infigratinib until resolved to CTCAE Grade ≤ 2, then
 
If resolved within ≤ 7 days, decrease by 1 dose level of infigratinib.
 
If not resolved within 7 days, discontinue subject from study drug
 
					
Grade 4	Discontinue infigratinib.					
Anemia *						
	ed RBC transfusion for hemoglobin < 7 g/dL, or < 8 g/dL for subjects ease, per AABB guidelines, or if the investigator suspects the subject is					
Grade 3 (hemoglobin < 8.0 g/dL)	Hold dose of infigratinib until resolved or corrected to CTCAE Grade ≤ 2 or baseline, then maintain dose level					
Grade 4	Hold dose of infigratinib until resolved or corrected to CTCAE Grade ≤ 2 or baseline, then decrease by 1 dose level					
Platelet Count Decreased (Thron	nbocytopenia) *					
Grade 3 (platelet < 50 to 25 × 10  /L) without	Hold dose of infigratinib until resolved to CTCAE Grade ≤ 2 or baseline					
≥ Grade 2 bleeding	
 
If resolved within ≤ 7 days, maintain dose level of infigratinib
 
If resolved between > 7 days and 14 days, decrease by
 
					
	

1 dose level of infigratinib

If not resolved within ≤ 14 days, discontinue infigratinib

					
Grade 3 (platelet < 50 to 25 × 10  /L) with bleeding	Hold dose of infigratinib until resolved to CTCAE Grade ≤ 2 or baseline, then decrease by 1 dose level					
or Grade 4 (platelet < 25 × 10  /L)	
 
If not resolved within ≤ 14 days, discontinue infigratinib
 
					

**Table 6.** Criteria for Interruption and Re-initiation of Infigratinib for AEs Considered to be Possibly Related to Infigratinib

	Possibly Related to Infigratinib					
Worst Toxicity CTCAE (v5.0) Grade (Unless Otherwise Specified)	Recommended Dose Modifications any Time During a Cycle of Therapy					
	INVESTIGATIONS – RENAL					
Serum Creatinine						
Grade ≥ 2	If serum creatinine CTCAE Grade ≥ 2 has been demonstrated in conjunction with hyperphosphatemia, serum creatinine levels must repeated at least weekly until resolution. 24-hour urine collection should be obtained as clinically indicated for total phosphate, calciuprotein, and creatinine clearance. Ultrasound examination of the kidneys should be performed as indicated to evaluate de-novo calcifications until resolution or stabilization of creatinine.					

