Grade 2 (≥ 2.00 to 3.0 × ULN or 2.0 to 3.0 × baseline)	
 
Hold dose of infigratinib until resolved to Grade ≤ 1 or baseline
 
If resolved within ≤ 7 days, maintain dose level of infigratinib
 
If resolved between > 7 days and 14 days, decrease by 1 dose level of infigratinib
 
If not resolved within ≤ 14 days, discontinue infigratinib
 
					
Grade ≥ 3 (> 3.0 × ULN or > 3 × baseline)	Discontinue infigratinib					
	INVESTIGATIONS – HEPATIC					
AST or ALT						
Grade 3 (> 5.0 to 20.0 × ULN) without bilirubin elevation > 2.0 × ULN	Hold dose of infigratinib until resolved to CTCAE Grade ≤ 1 or baseline  • If resolved within ≤ 7 days, decrease by 1 dose level of infigratinib  • If not resolved within ≤ 7 days, discontinue infigratinib					
Grade 4 (> 20.0 × ULN) without bilirubin elevation > 2.0 × ULN	Discontinue infigratinib					
AST or ALT and Bilirubin						
AST or ALT > 3.0 to 5.0 × ULN and total bilirubin > 2.0 × ULN without liver metastasis or evidence of disease progression in the liver	
 
Hold dose of infigratinib until both transaminases and bilirubin resolved to CTCAE Grade ≤ 1 or baseline.
 
If resolved within ≤ 7 days, decrease by 1 dose level of infigratinib.
 
If not resolved within ≤ 7 days, discontinue infigratinib
 
					
AST or ALT > 5.0 × ULN and total bilirubin > 2.0 × ULN	Discontinue infigratinib					

**Table 6.** Criteria for Interruption and Re-initiation of Infigratinib for AEs Considered to be Possibly Related to Infigratinib

Worst Toxicity CTCAE (v5.0) Grade (Unless Otherwise Specified)	Recommended Dose Modifications any Time During a Cycle of Therapy						
LABORATORY / METABOLIC DISORDERS							
Asymptomatic Amylase and/or I	ipase Elevation						
present, consider a CT scan or oth	nptoms of acute pancreatitis (abdominal pain or tenderness), and, if er imaging study to assess the pancreas, liver, and gallbladder to creatitis and assess for complications.						
Grade 3 (> 2.0 to 5.0 × ULN)	Hold dose of infigratinib until resolved to CTCAE Grade ≤ 2						
	decrease by 1 dose level of infigratinib						
	
 
If not resolved within ≤ 14 days, discontinue infigratinib
 
						
	For recurrent Grade 3 asymptomatic lipase or amylase elevation despite dose reduction, infigratinib should be held and continuation of therapy should be discussed with the medical monitor following resolution to ≤ Grade 2.						

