#### Score Definition

- 0 Fully active, able to carry on all pre-disease activities without restriction
- 1 Restricted in physically strenuous activity but ambulatory and able to carry out work of a light or sedentary nature, eg, light house work or office work
- 2 Ambulatory and capable of all selfcare but unable to carry out any work activities. Up and about more than 50% of waking hours
- 3 Capable of only limited selfcare, confined to bed or chair more than 50% of waking hours
- 4 Completely disabled. Cannot carry on any selfcare. Totally confined to bed or chair
- 5 Dead
- 5. Vital signs: Blood pressure, pulse rate, and body temperature to be recorded in the same position, either supine or sitting.
- **6. Hematology:** No need to repeat on C1D1 if baseline assessment performed within 72 hours prior to that date. On treatment, to be performed prior to dosing with study medications unless otherwise indicated. Lab abnormalities that are adverse events specified in Table 6 must be followed at least weekly until resolution to the grade specified in Table 6.
- 7. Complete metabolic panel: No need to repeat on C1D1 if baseline assessment performed within 72 hours prior to that date. Lab abnormalities that are adverse events specified in Table 6 must be followed at least weekly until resolution to the grade specified in Table 6.
- **8. Amylase**, **lipase**: No need to repeat on C1D1 if baseline assessment performed within 72 hours prior to that date. Lab abnormalities that are adverse events specified in Table 6 must be followed at least weekly until resolution to the grade specified in Table 6.
- **9.** Calcium, magnesium, phosphorus (serum): No need to repeat on C1D1 if baseline assessment performed within 72 hours prior to that date. Lab abnormalities that are adverse events specified in Table 6 must be followed at least weekly until resolution to the grade specified in Table 6.
- **10. Urinalysis:** Macroscopic or microscopic.
- **11. Pregnancy Test:** For female subjects of childbearing potential, a serum or urine pregnancy test must be performed within 7 days of first day of study drug and at end-of-treatment. Additional pregnancy test to be repeated when potential pregnancy is suspected.

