#### 10. MEASUREMENTS

### 10.1 Primary endpoint:

The primary endpoint is the incidence of dose-limiting toxicities (DLTs) in the first 2 cycles of therapy at a specific dose. In Cohort 1, in a subset of subjects who start at infigratinib 100 mg and complete 2 cycles with no DLTs and who remain on study for Cycles 3 and 4, the dose of infigratinib will be increased to 125 mg starting with Cycle 3 and the number of DLTs in Cycles 3 and 4 will be counted toward the primary endpoint (for the 125 mg dose), in addition to the number of DLTs in Cycles 1 and 2 (for the 100 mg dose). For all other subjects, the primary endpoint will be the number of DLTs in Cycles 1 and 2.

DLTs will be graded using NCI CTCAE (Common Terminology Criteria for Adverse Events), v5.0. DLTs will be defined as an adverse event (AE) or abnormal laboratory value at least possibly related to therapy with infigratinib including those AEs and abnormal laboratory values that result in a failure to meet the criteria for re-treatment. The criteria for defining a DLT, which are pre-specified based on the pre-clinical toxicity of infigratinib, are listed in Table 7.

Individual subjects who had a DLT may be retreated, after recovery, at the next lowest dose level.

Investigators will notify QED Therapeutics within 7 days of any DLTs observed.

**Table 7.** Criteria for defining dose-limiting toxicities

TOXICITY	DLT CRITERION
Skipped/ delayed dose	The inability to administer infigratinib on ≥ 75% of scheduled treatment days during cycle 1 at that dose (ie, ≥ 16 days of the 21 days of planned treatment) due to unresolved adverse event of any grade and considered at least possibly, probably, or definitely related to the study drug.
	Delay in 2 nd cycle administration at that dose due to failure of recovery from a possibly, probably, or definitely related adverse event to Grade ≤ 1 or baseline by Day 43 (Day 28 of Cycle 1 + 15 days), except for alopecia.
Blood/ bone marrow	Neutropenia     • Febrile, CTCAE Grade ≥ 3.     • CTCAE Grade ≥ 3 for > 7 consecutive days
	Thrombocytopenia
	Anemia CTCAE Grade 4
Renal/ genitourinary	Creatinine:  • CTCAE Grade 1 for > 7 consecutive days and serum inorganic phosphorus  > 5.5 mg/dL and/or serum total calcium x serum inorganic phosphorus  > 55 mg²/dL² and despite phosphorus lowering therapy for ≥ 14 days
	
 
CTCAE Grade 2 for > 7 consecutive days
 
CTCAE Grade ≥ 3
 

**Table 7.** Criteria for defining dose-limiting toxicities

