TOXICITY	DLT CRITERION	
Hepatic	Bilirubin: • CTCAE Grade 2 for > 7 consecutive days	
	• CTCAE Grade ≥ 3	
	AST or ALT: • Grade 3 for > 7 consecutive days • CTCAE Grade 4	
	Hy's Law	
	
 
ALT or AST ≥ 3 x upper limit of normal (ULN)
 
AND
 
Serum total bilirubin > 2 x ULN
 
	
	For patients with known hepatic metastases:  • AST or ALT > 8 x ULN  OR	
	• AST or ALT > 5 x ULN for ≥ 14 days	
Pancreas	Pancreatitis CTCAE Grade ≥ 2	
	Amylase/lipase (serum-high): CTCAE Grade ≥ 3 asymptomatic amylase and/or asymptomatic lipase not reversible to CTCAE Grade ≤ 2 within 7 days	
Cardiac	QTcF interval > 500ms	
	Other cardiac CTCAE Grade ≥ 3	
Constitutional	Fatigue CTCAE Grade 3 for > 7 consecutive days	
	Fatigue CTCAE Grade 4	
Ocular/visual	Any ocular/visual toxicity CTCAE Grade ≥ 3.	
Gastrointestinal	CTCAE Grade 3 or 4 nausea/vomiting and/or diarrhea despite the use anti-emetic and anti-diarrhea therapy, respectively	
Metabolic/ laboratory	
 
Hyperphosphatemia (serum-high):
 
Serum inorganic phosphorus > 7.0 mg/dL for > 7 consecutive days despite phosphorus-lowering therapy for at least 14 days.
 
Serum inorganic phosphorus > 9.0 mg/dL, despite phosphorus-lowering therapy for at least 14 days.
 
Serum inorganic phosphorus > 10.0 mg/dL
 
Hypercalcemia (serum-high)
 
Serum calcium CTCAE Grade 2 for > 7 consecutive days.
 
Serum calcium CTCAE Grade ≥ 3.
 
	
Other	Any death not clearly due to the underlying disease or known, extraneous causes.	
	Clinical evidence for any grade (CTCAE Grade ≥ 1) of ectopic, de-novo -calcification within the soft tissue including the peri-articular spaces and vascular as well as visceral tissues (eg, kidney, lung, stomach, myocardium, etc.)	
	
 
Any other CTCAE Grade 3 or 4 non-hematological toxicity except with following exclusions:
 
• Alkaline phosphatase CTCAE Grade ≥ 3.
 
• Lymphocytopenia CTCAE Grade ≥ 3 unless considered clinically significant.
 
	

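### Weekly laboratory follow-up stops at Table 6, so two duration-based DLTs in Table 7 (isolated Grade 2 bilirubin and conditional Grade 1 creatinine) are not reliably ascertained

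*Combined protocol and SAP*

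**What the plan says.** **Follow-up rules.** Section 6 states: "Adverse event lab abnormalities outlined in Table 6 should be followed at least weekly until the specified resolution". Section 9, footnotes 6 to 9, repeats the rule for each laboratory group: abnormalities that count as adverse events under Table 6 "must be followed at least weekly until resolution to the grade specified in Table 6". Both refer to Table 6 only.

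**Table 6 (Section 6).** The lowest creatinine grade with a dose-modification row is "Grade 2 (≥ 2.00 to 3.0 × ULN or 2.0 to 3.0 × baseline". The action there is "Hold dose of infigratinib until resolved to Grade ≤ 1 or baseline", so Grade 1 counts as resolved. The creatinine-specific weekly repeat begins "If serum creatinine CTCAE Grade ≥ 2 has been demonstrated in conjunction with hyperphosphatemia". Bilirubin appears only jointly with raised AST or ALT. The catch-all row for other clinically significant events covers Grades 3 and 4.

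**Table 7 (Section 10.1).** The bilirubin row makes "CTCAE Grade 2 for > 7 consecutive days" a DLT. The creatinine row begins "CTCAE Grade 1 for > 7 consecutive days and serum inorganic phosphorus". It requires phosphorus above 5.5 mg/dL and/or a calcium-phosphorus product above 55, despite at least 14 days of phosphorus-lowering therapy.

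**Use of the count.** Under Section 12.4, a dose with no DLT in 3 subjects or 1 in 6 is declared safe. For subjects escalated from 100 mg, DLTs in Cycles 3 and 4 count toward 125 mg.

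**The concern.** A criterion based on more than 7 consecutive days needs draws spaced to show it. For most duration-based laboratory DLTs the weekly rule supplies them. For isolated Grade 2 bilirubin and Grade 1 creatinine it does not, and the next required value is the next scheduled panel.

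DLT incidence is the primary endpoint and the only input to the dose decision. An unseen DLT can turn 1 of 3 into 0 of 3, or 2 of 6 into 1 of 6. The gap is widest in Cycles 3 and 4, where much of the evidence on 125 mg may be gathered.

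**Working it through.** The documents give no figure to reproduce here, because the sample size has no formal basis (Section 12.1).

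**1. Coverage, Table 7 against Table 6**

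| Duration-based laboratory DLT | Row in Table 6? |
|---|---|
| Neutropenia Grade ≥ 3; creatinine Grade 2; AST/ALT Grade 3; amylase/lipase Grade ≥ 3; phosphorus > 7.0 mg/dL; calcium Grade 2 | Yes |
| Bilirubin Grade 2, isolated | No (only with AST/ALT) |
| Creatinine Grade 1, conditional | No (starts at Grade 2) |

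The thrombocytopenia entry in Table 7 is not legible in the text available and was not assessed.

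**2. Gaps between scheduled metabolic panels (Section 9 calendar)**

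Assumption: the panel includes creatinine and bilirubin, since its contents are not listed. Nominal study days are 1, 4, 15, 29, 43 and 57 (Cycle 3 Day 1). From Cycle 3 there is a Day 1 panel only: Days 57, 85 and 113.

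- Day 4 to 15: 11 days. With windows of ±1 and ±3: 11 − 4 = 7 to 11 + 4 = 15.
- Day 15 to 29, 29 to 43 and 43 to 57: 14 days each. With windows: 14 ± 6 = 8 to 20.
- Cycles 3-4: 28 days. With windows: 28 ± 6 = 22 to 34.

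**3. What these panels can show**

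Take an episode of L days starting at s, abnormal throughout [s, s + L). Two draws g days apart both fall inside it only if L > g. From Day 4 the smallest gap is 11 days, so every episode of 8 to 11 days gives 0%. For other lengths, assume nominal visit days and onset uniform from Day 2 to Day 49, a range of 47 days:

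- L = 8, seen at all: onset must fall within 8 days before a draw. The qualifying days are 2 (Day 4 draw, cut off at Day 2) + 8 + 8 + 8 + 0 = 26, and 26/47 = 55%. So 45% miss every panel.
- L = 14, two abnormal values: only the Day 4 and Day 15 pair qualifies, 2/47 = 4%.
- L = 21: (2 + 7 + 7 + 7)/47 = 23/47 = 49%.

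In Cycles 3-4 no episode of 28 days or less gives two abnormal scheduled values. With uniform onset, an 8-day episode misses every draw in 1 − 8/28 = 71% of cases.

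**4. Timing of the creatinine row**

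The first on-treatment phosphorus check that can start therapy is Cycle 1 Day 4 (Section 4.1.2), so the 14-day condition is met from about Day 4 + 14 = 18. The later panels in Cycles 1-2 are Days 29, 43 and 57. Days 29 and 57 follow the drug-free weeks (Days 22-28 and 50-56), and Section 7.1.1 says hyperphosphatemia normalizes rapidly off drug. Only Day 43 is an on-drug panel.

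**5. Effect of an added repeat** (same assumptions; repeat counted from the first abnormal scheduled panel)

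| Episode (days) | Two abnormal scheduled values > 7 days apart | Still abnormal at +7 days | Still abnormal at +8 days |
|---|---|---|---|
| 8 | 0% | 9% | 0% |
| 10 | 0% | 23% | 17% |
| 14 | 4% | 49% | 43% |
| 21 | 49% | 100% | 94% |

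A value at exactly +7 days does not strictly show more than 7 days, which is why one later repeat is needed.

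**6. Sensitivity of the 3+3 rule** (assumed rates only)

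P(declared safe) = (1 − p)³ + 3p(1 − p)² × (1 − p)³, where p is the observed DLT rate.

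| True DLT rate | None unseen | 10% of DLTs unseen | 25% of DLTs unseen |
|---|---|---|---|
| 20% | 71% | 75% | 81% |
| 30% | 49% | 56% | 65% |
| 40% | 31% | 38% | 49% |

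These show direction and sensitivity. They are not estimates for the two rows.

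**The case against.** The strongest reply is that this is a narrow wording gap that practice would largely close. Unscheduled visits are allowed, and Section 7.3 records start and end dates for each adverse event. Two consecutive abnormal panels 11 or 14 days apart would themselves indicate persistence beyond 7 days.

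The creatinine row is also compound. Phosphorus above 5.5 and up to 7.0 mg/dL is a Table 6 row, and above 7.0 mg/dL checks are due every 2 to 3 days, so many of these subjects would be having blood drawn anyway. A missed event matters only if it is that subject's sole DLT and the count is at a boundary.

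Much of this stands. A reader might infer that more than 7 days cannot be observed at all for these rows. The documents do not support that, because longer episodes can be seen and extra draws may be taken. What remains is that none is required. Phosphorus checks do not mandate creatinine, and the calcium-phosphorus limb can be met at phosphorus of 5.5 mg/dL or below. Recorded dates are only as good as the draws behind them, and Section 7.2 does not treat every abnormal value as an adverse event.

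A reader might also turn the 103 of 433 subjects with raised creatinine (Table 1) into 12 × 103/433 = 2.9 of 12 subjects, or a 1 − (1 − 0.238)³ = 56% chance of at least one in three. Those are not rates of this DLT. The 103 covers any grade and any duration, on monotherapy and regardless of relationship, without the phosphorus and 14-day conditions.

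**Conclusion.** The point holds as a gap in ascertainment. Two DLTs in the primary endpoint have no required repeat, and the scheduled panels do not reliably show whether they lasted more than 7 days. At nominal Cycle 1-2 visits, episodes of 8 to 11 days are never shown to qualify, 14-day episodes in about 4% of cases and 21-day episodes in about 49%. In Cycles 3-4 the panels are 28 days apart. The percentages rest on uniform onset, nominal visit days, continuous abnormality and no unscheduled draws.

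The likely direction is under-counting of DLTs, which favors declaring a dose safe. The size is unknown, because the documents give no rate for either DLT on the combination. For bilirubin they give only Grade 3 or 4 increases, in 6 of 433 subjects (1.4%, Table 2). This is a cheap improvement. It does not show that the dose decision would be wrong.

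**What to change.** In Section 6 and in Section 9, footnotes 6 to 9, extend the at-least-weekly repeat to any laboratory abnormality with a duration-based criterion in Table 7. Apply it throughout each DLT window, including Cycles 3 and 4 for subjects escalated to 125 mg. Require one repeat more than 7 days after the first abnormal value, so that the criterion can be shown to be met or not met.

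Leave the DLT thresholds unchanged. In particular, do not replace the added draws with a rule that counts from the first abnormal value to the first recovered one. With panels 11 or 14 days apart from Day 4, that would make every single transient value a DLT. Counting a value still abnormal on day 7 would change the criterion from more than 7 days to at least 7.

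The sponsor should reconcile Table 6, Table 7 and the calendar. That includes phosphorus between 5.5 and 7.0 mg/dL, where the weekly rule appears to apply through Table 6 but Section 4.1.2 starts increased monitoring only above 7.0.

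The cost is wording, a few extra blood draws and possibly a slightly higher DLT count. The change narrows the gap without closing it, since onset between panels is still unseen.
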